4.1. Inclusion Criteria*

- (1) Complete 12 months of treatment with LMIS 50 mg under Protocol FP01C-13-001. If a subject wishes to enter the Extension study after more than 28 days following his end of study visit for Protocol FP01C-13-001, his serum testosterone level should be repeated at the screening visit to confirm that his castrate-level testosterone has been maintained.
- (2) Laboratory values
 - o Absolute neutrophil count \geq 1,500 cells/ μ L
 - o Platelets \geq 100,000 cells/ μ L
 - o Hemoglobin \geq 10 gm/dL
 - o Total bilirubin \leq 1.5 \times upper limit of normal (ULN)
 - o AST (SGOT) \leq 2.5 \times ULN
 - o ALT (SGPT) \leq 2.5 \times ULN
 - o Serum creatinine \leq 1.5 mg/dL
 - o Lipid profile within acceptable range according to investigator's opinion
 - o Serum glucose within acceptable range according to investigator's opinion
 - o HgbA1c within acceptable range according to investigator's opinion
 - o Clinical chemistries (K, Na, Mg, Ca and P) within acceptable range according to investigator's judgment
 - o Urinalysis within normal range according to the investigator's judgment
- (3) Agree to use male contraceptive methods during study trial
- (4) In the Investigator's opinion, the ability to understand the nature of the study and any hazards of participation, and to communicate satisfactorily with the Investigator and to participate in, and to comply with, the requirements of the entire protocol
- (5) All aspects of the protocol explained and written informed consent obtained

*If the patient completed 12 months of treatment with LMIS 50 mg more than 28 days prior to entering the Extension study, the ECOG, PE, ECG, laboratory and PSA tests should be repeated.

If the patient has completed 12 months of treatment with LMIS 50 mg under Protocol FP01C-13-001 within the last 28 days, they will be allowed to enter the Extension study without repeating the testosterone measurements, ECG, PE, laboratory and the PSA tests

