5.1. Treatment plan summary

Subjects enrolled in this open-label, phase IIIb safety extension study will receive a single subcutaneous injection of LMIS 50mg every 6 months for up to 2 doses.

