(10) Record any pre-treatment AE(s) NOTE: Open AEs from Protocol FP01C-13-001 will be recorded in this study file and noted in the database and other study documentation as, "AE under Protocol FP01C-13-001." These AEs should not be counted twice in the overall safety database.

*If the patient completed 12 months of treatment with LMIS 50 mg more than 28 days prior to entering the Extension study, the testosterone level should be repeated and the repeat test should indicate that the patient maintains a castrate-level of testosterone. In addition, the ECOG, PE, ECG, laboratory and PSA tests should be repeated.

If the patient has completed 12 months of treatment with LMIS 50 mg under Protocol FP01C-13-001 within the last 28 days, they will be allowed to enter the Extension study without repeating the testosterone measurements, ECG, PE, laboratory and the PSA tests.

6.2. Day 0 (approximately 6 months from last dose of LMIS 50 mg under Protocol FP01C-13-001)

Perform the following at 0 hr:

- (1) Record subject enrollment number prior to dosing (same enrollment number as was used in FP01C-13-001 will be used in this study)
- (2) Record vital signs prior to dosing
- (3) Record concomitant medication(s) prior to dosing
- (4) Record AE(s) prior to dosing and post dosing
- (5) Administer LMIS 50 mg.

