9. EXTENT OF EXPOSURE AND DRUG COMPLIANCE

The treatment duration (days) is defined as (last administered date – first administered date + 1); and the study duration (days) is defined as (last visit date – first administered date + 1).

The treatment duration (days) and study duration (days) will be summarized by the number of observations (n), mean, median, standard deviation (SD), standard error, minimum and maximum. The summary results will be presented as Table 14.3.2. Also, the proportion of subjects received first and second administration has been provided as Table 14.3.2.

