10. SAFETY ANALYSIS

10.1 Adverse Events

All AEs (whether treatment related or not) that occur before, during, or after dosing of the study medication will be recorded. The verbatim adverse event (AE) terms will be coded using the MedDRA dictionary, version18.1 or highest, and classified by System Organ

Statistical Analysis Plan

Class and Preferred Term.

Adverse events will be categorized as:

- Previous treatment-emergent adverse event (TEAE): The TEAEs are captured from previous FP01C-13-001 study.
- Newly treatment-emergent adverse event (TEAE): AEs occurring during or after the treatment period until the subject is off study, or before the first administration of study drug and worsen in severity for this FP01C-13-001-EX study.

Total treatment-emergent adverse event (TEAE): The combination of previous TEAEs and Newly TEAEs.

Unless otherwise specified, all adverse event summaries will include the previous TEAEs, Newly TEAEs and Total TEAEs. The listing of all TEAEs will be provided in Listing 16.2.7.1.

All AEs will be summarized by CTCAE version 4 grade and MedDRA preferred terms. The severity will be graded as follows:

- Grade 1 Mild; asymptomatic or mild symptoms; clinical or diagnostic observations only; intervention not indicated
- Grade 2 Moderate; minimal, local or noninvasive intervention indicated; limiting age-appropriate instrumental activities of daily living* (ADL)
- Grade 3 Severe or medically significant but not immediately life-threatening; hospitalization or prolongation of hospitalization indicated; disabling; limiting self-care ADL**
- Grade 4 Life-threatening consequences; urgent intervention indicated
- Grade 5 Death related to AE

Activities of Daily Living (ADL):

*Instrumental ADL refer to preparing meals, shopping for groceries or clothes, using the telephone, managing money, etc.

**Self-care ADL refer to bathing, dressing and undressing, feeding self, using the toilet, taking medications, and not bedridden.

The reasonable possibility of causation will be determined based on the investigator's clinical judgment as follows:

- **Definite:** A clinical event, including laboratory test abnormality, occurring in a plausible time relationship to drug administration, and which cannot be explained by concurrent disease or other drugs or chemicals.

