TEAEs by relationship									
Definite	E	nn	(xx.x%)	E	nn	(xx.x%)	E	nn	(xx.x%)
Possible	E	nn	(xx.x%)	E	nn	(xx.x%)	E	nn	(xx.x%)
Unrelated	E	nn	(xx.x%)	E	nn	(xx.x%)	E	nn	(xx.x%)
Drug-related AEs*									
	E	nn	(xx.x%)	E	nn	(xx.x%)	E	nn	(xx.x%)
Drug-related AEs* by severity									
Mild	E	nn	(xx.x%)	E	nn	(xx.x%)	E	nn	(xx.x%)
Moderate	E	nn	(xx.x%)	E	nn	(xx.x%)	E	nn	(xx.x%)
Severe	E	nn	(xx.x%)	E	nn	(xx.x%)	E	nn	(xx.x%)
Life-threatening	E	nn	(xx.x%)	E	nn	(xx.x%)	E	nn	(xx.x%)
Death	E	nn	(xx.x%)	E	nn	(xx.x%)	E	nn	(xx.x%)
SAEs									
	E	nn	(xx.x%)	E	nn	(xx.x%)	E	nn	(xx.x%)

E is the number of events, n is the number of subjects, and the AE percentage: 100%*The number of subjects with event (n) / Total number of subjects in Safety population (N)

*Relationship to study drug: AE related to study drug will include AEs classified as 'Definite', or 'Possible'. AEs not related to study drug will include AEs that is 'Unrelated'.

[Program: \\Foresee\\FP01C-13-001\\SAP\\Table\\S_AE.sas]

Table 14.3.1.2: Summary of Incidence of TEAEs (Safety Population)

System Organ Class / Preferred Term	Previous TEAEs (N=XX)			Newly TEAEs (N=XX)			Total TEAEs (N=XX)		
	E	n	(%)	E	n	(%)	E	n	(%)
System Organ Class 1									
Preferred Term 1	E	nn	(xx.x%)	E	nn	(xx.x%)	E	nn	(xx.x%)
Preferred Term 2	E	nn	(xx.x%)	E	nn	(xx.x%)	E	nn	(xx.x%)
System Organ Class 2									
Preferred Term 1	E	nn	(xx.x%)	E	nn	(xx.x%)	E	nn	(xx.x%)
Preferred Term 2	E	nn	(xx.x%)	E	nn	(xx.x%)	E	nn	(xx.x%)

E is the number of events, n is the number of subjects, and the AE percentage: 100%*The number of subjects with event (n) / Total number of subjects in Safety population (N)
 [Program: \\Foresee\\FP01C-13-001\\SAP\\Table\\S_AE.sas]

Table 14.3.1.3: Summary of Incidence of TEAEs by Severity (Safety Population)

			Previous TEAEs (N=XX)			Newly TEAEs (N=XX)			Total TEAEs (N=XX)		
	System Organ Class	Preferred Term	E	n	(%)	E	n	(%)	E	n	(%)
Mild AE											
	System Organ Class 1	Preferred Term 1	E	nn	(xx.x%)	E	nn	(xx.x%)	E	nn	(xx.x%)
	System Organ Class 1	Preferred Term 2	E	nn	(xx.x%)	E	nn	(xx.x%)	E	nn	(xx.x%)
	System Organ Class 2	Preferred Term 1	E	nn	(xx.x%)	E	nn	(xx.x%)	E	nn	(xx.x%)
	System Organ Class 2	Preferred Term 2	E	nn	(xx.x%)	E	nn	(xx.x%)	E	nn	(xx.x%)
Moderate AE											
	System Organ Class 1	Preferred Term 1	E	nn	(xx.x%)	E	nn	(xx.x%)	E	nn	(xx.x%)
	System Organ Class 1	Preferred Term 2	E	nn	(xx.x%)	E	nn	(xx.x%)	E	nn	(xx.x%)
	System Organ Class 2	Preferred Term 1	E	nn	(xx.x%)	E	nn	(xx.x%)	E	nn	(xx.x%)

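### AE percentages for Previous, Newly and Total events share one N but cover unequal follow-up, so they cannot be compared between columns without person-time

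*SAP*

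**What the plan says.** SAP 10.1 states that, unless otherwise specified, "all adverse event summaries will include the previous TEAEs, Newly TEAEs and Total TEAEs". The footnote to Table 14.3.1.1, repeated under every AE shell to Table 14.3.1.10, gives "the AE percentage: 100%*The number of subjects with event (n) / Total number of subjects in Safety population (N". It also explains that "E is the number of events, n is the number of subjects", so event counts are shown but are not divided by exposure.

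The three columns cover different periods:

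- **Previous.** SAP 10.1 says only "The TEAEs are captured from previous FP01C-13-001 study". Protocol 4.1 requires each man to "Complete 12 months of treatment with LMIS 50 mg under Protocol FP01C-13-001", so everyone in this column has a finished parent year. Protocol 6.1 adds that "Open AEs from Protocol FP01C-13-001 will be recorded in this study file" and says nothing there about parent-study AEs that had resolved.
- **Newly.** The window ends when the man leaves the study, at the latest at the Day 336±7 visit (Protocol 6.6). Treatment is "every 6 months for up to 2 doses" (Protocol 5.1). Protocol 1.3 and 5.6 let dosing and safety follow-up continue only to the expiry date of the trial material.
- **Total.** The two combined.

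SAP 9 defines study duration from first extension dose to last visit, and says "the proportion of subjects received first and second administration has been provided as Table 14.3.2". These summaries cover the extension only and do not feed the AE tables.

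**The concern.** A crude percentage depends on how long people were watched as well as on how often events occur. Three such percentages in adjacent columns, all on the same N, invite comparison. When the periods differ in length, a difference between columns can come from follow-up alone. Safety over up to one extension year and two years of total exposure is the study's only objective, and these are its main AE tables. Protocol 10.3 speaks of incidence rates, yet no shell has time in a denominator. A reader could recover a rough extension event rate from the event counts and Table 14.3.2. No planned table gives parent-period exposure, so the same cannot be done for Previous or Total.

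**Working it through.** The documents give no AE rate, dropout rate or AE duration, so there is no planned figure to reproduce. The 30% risk, the dropout shares and the mean durations below are assumptions.

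**1. How long extension follow-up can be.** Inputs are the protocol date of 01 Oct 2015 (SAP 1), taken as the earliest possible Day 0, and the two expiry dates in Protocol 1.3 and 5.6: 31 May 2016 (current) and 30 Nov 2016 (expected by the sponsor, not guaranteed).

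| Expiry date | Days from 01 Oct 2015 | Latest Day 0 to reach Day 336 | Latest Day 0 for a Day 168 dose |
|---|---|---|---|
| 31 May 2016 | 243 | 30 Jun 2015 | 15 Dec 2015 |
| 30 Nov 2016 | 426 | 30 Dec 2015 | 15 Jun 2016 |

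On the current date, if the clause is applied as written, nobody dosed on or after 01 Oct 2015 reaches Day 336.

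**2. Constant rate, all parent-study events in Previous.** Take a 30% risk over 336 days: λ = −ln(1 − 0.30)/336 = 0.001062 per day. The risk over t days is 1 − exp(−λt).

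- t = 336: 30.0%
- t = 243: 1 − exp(−0.2580) = 22.7%
- t = 168: 1 − √0.70 = 16.3%
- Total, 672 days: 1 − 0.70² = 51.0%

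If the parent year is 365.25 days and carries the 30% risk, full extension follow-up to Day 336 gives 1 − 0.70^(336/365.25) = 28.0%.

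**3. Dropout alone.** Let a share d leave at an exponential rate μ = −ln(1 − d)/336. The crude percentage is λ/(λ + μ) × [1 − exp(−(λ + μ) × 336)]. For d = 10%, 20% and 30% it is 28.6%, 27.1% and 25.5%. For d = 30%, for example, λ = μ, so the result is 0.5 × (1 − 0.49) = 25.5%.

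**4. Only open events in Previous.** With mean AE duration m days, the chance of at least one event open at day 336 is 1 − exp(−λm[1 − exp(−336/m)]). For m = 14, 30 and 90 days, Previous reads 1.5%, 3.1% and 8.9%. Newly reads 30.0% at 336 days or 16.3% at 168 days, so a constant rate now looks as if it rises.

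**5. With person-time.** Take N = 137, the maximum in SAP 4.3, and the same λ. Expected events are 137λt and person-years are 137t/365.25.

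| Days | Crude n/N | Expected events | Person-years | Events per 100 person-years |
|---|---|---|---|---|
| 336 | 30.0% | 48.9 | 126.0 | 38.8 |
| 243 | 22.7% | 35.3 | 91.1 | 38.8 |
| 168 | 16.3% | 24.4 | 63.0 | 38.8 |

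First events give the same rate when each man's time stops at his first event. At 336 days, 137 × 0.30 = 41.1 men over 41.1/0.3877 = 106.0 person-years is 38.8 per 100.

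**The case against.** A reader might infer that a constant AE rate will appear to fall in year 2. The documents do not support this. It needs Previous to mean all parent-study events, which SAP 10.1 does not say and which the recording rule in Protocol 6.1 leaves open. It also needs materially shortened follow-up. Missing the second injection is not a withdrawal criterion (Protocol 4.3) and scheduled visits run to Day 336, so no text fixes one-dose follow-up at 168 days. No document says how many men will receive one dose. The sponsor expects the later expiry date. Dropout on its own moves the figure little.

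The sponsor can add that the objective is descriptive, that no test of year 1 against year 2 is planned, and that event counts, doses received, study duration and attendance by visit are all reported. This is correct, and it limits the harm. It does not supply parent-period exposure or make the three percentages comparable.

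Exposure adjustment also has limits. Everyone in Previous completed year 1, so men whose events ended parent participation are absent by selection, and person-time cannot repair that. Telephone contacts after early termination collect only drug-related AEs (Protocol 3.1), so counting time to the last call would dilute rates for all AEs.

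The SAP also plans no interval estimates. No events in 137 men, for instance, has an exact 95% upper limit of 1 − 0.025^(1/137) = 2.7%. That concerns precision and is not evidence of unequal follow-up.

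**Conclusion.** The point holds conditionally. The three columns cannot be compared as crude n/N, because they share an N and differ in follow-up. The direction and size of any distortion are not fixed by the documents. For an assumed 30% risk at a constant rate, with all parent-study events counted and a 336-day parent period, Newly could read 22.7% (243 days) or 16.3% (168 days). With 10% to 30% dropout it would read 28.6% to 25.5%, and with full follow-up there would be no gap. If only open events are counted, Previous could instead read far below Newly. The expiry clause makes shortened follow-up a real possibility, but the result depends on which date applies and when men were first dosed. Rates beside n/N are a better method at small cost. The change should be made, but the plan does not fail without it.

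**What to change.** 1. In SAP 10.1, define Previous as all parent-study treatment-emergent AEs of men in the extension safety population.
2. Keep n/N. In Tables 14.3.1.1, 14.3.1.2, 14.3.1.4 and 14.3.1.6, add for each column the person-years at risk and the men with a first event per 100 person-years, with exact Poisson 95% limits. Event counts per 100 person-years may also be shown, but without Poisson limits, because events repeat within a man.
3. Take Previous person-time from parent-study dosing and visit dates. Take Newly person-time from first extension dose to last visit, which is the SAP 9 study duration, and not to the last telephone contact. Count in the rates only events with onset inside those windows.
4. Footnote that n/N is not comparable between columns, and that a year-1 against year-2 contrast is affected by selection even after exposure adjustment, because every man in Previous completed year 1.

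The cost is SAP wording, a merge of parent-study dates for the safety population, and extra columns in four tables. No new data are collected.
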